12.1.2. Statistical Analysis Plan

All imaging endpoints will be statistically evaluated using linear mixed models (LMMs: Laird and Ware, 1982). LMMs are advantageous for longitudinal clinical trials because they can account for the dependency due to repeated measures with relatively few parameters, which potentially enhances statistical efficiency. Furthermore, LMMs can accommodate incomplete cases (i.e., missing data), which is expected in this study due to dropout. LMMs are typically estimated using maximum likelihood methods (Verbeke and Molenberghs, 2000) that yield valid inferences with incomplete cases under the widely applicable assumption that the missing data are ignorable (Little and Rubin 2002). For all analyses, the residuals of the fitted statistical models will be examined for evidence of departure from assumptions, such as normality. If assumptions appear to be grossly violated, then transformations of response variables might be considered. Alternatively, generalized LMMs might be used because of their ability to accommodate a wider range of distributional forms (e.g., beta distribution). The primary analysis will be conducted using a modified intent-to-treat analysis, which includes all subjects who are randomized, receive at least one dose of study medication in the double-blind phase, and meet the conditions specified in 12.1.1. Since this is a phase II proof of concept study, statistical significance will be determined by any test that exceeds the 0.10 significance level. To account for baseline imbalance due to randomization vagaries, the baseline group means (intercepts) in the statistical analysis will be constrained to be equal.

Primary Objective #1: *To evaluate the activity of Ibudilast (MN-166 100 mg/d) versus placebo at two years, as measured by quantitative magnetic resonance imaging (MRI) analysis for whole brain atrophy using brain parenchymal function (BPF).*

The first primary objective of the proposed study is to evaluate the activity of ibudilast (treatment) versus placebo. For the first primary objective, the endpoint is the rate of change in brain parenchymal fraction (BPF) of the treatment group versus the placebo group. The evaluation of activity is defined as the test of the null hypothesis that the BPF rates of change in

the treatment and placebo groups are equal. The null hypothesis can be evaluated based on parameter estimates in the LMM, the details of which are now presented.

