Longitudinal measurements will span up to five time points per participant (Baseline and 24, 48, 72, 96 weeks), and there is a possibility that BFP trajectories will not be linear. In order to assess the sensitivity of the results to the assumption of linearity, non-linear trends will be modeled with polynomials and compared to the fit of the linear trend model of Equation (1). If polynomials of order greater than one are required, then the evaluation of T versus P involves parameters in addition to δ from Equation (1), for example, the difference in quadratic terms. In this case, an appropriate Wald test will be performed, which is the multiparameter extension of the Z -test. Interpretation of the results will be in terms of T versus P differences in instantaneous rate of change (ie, the first derivative) at different time points.

Accounting for multiple sites. The proposed study involves multiple sites, which is a potential source of additional variation. Patients within a site tend to be correlated due to similarity of environment, eg, because of testing by the same set of clinicians (Localio et al 2001). It is potentially important to account for the nesting of patients within sites in order to produce proper precision estimates (ie, standard errors) for statistical testing. To account for site variation, the Equation (1) model may be augmented with additional random effects and associated variance components.

Suppose that Y_{hij} is BPF for the j th score of the i th patient in the h th site ($h = 1, \dots, S$). Then the LMM has the form in the left side of the table below. The right hand side of the table identifies the types of effects in each piece of the equation.

Linear Mixed Model with Site Effects

Equation	Types of Effects
$Y_{hij} = \alpha_p + \beta_p t_{hij} + (\gamma + \delta t_{hij}) g_{hi}$	[fixed effects]
$+ (a_{hi} + b_{hi} t_{hij})$	[patient random effects]
$+ (a_h + b_h t_{hij} + c_h g_{hi} + d_h g_{hi} t_{hij})$	[site random effects]
$+ \epsilon_{hij}$	[random error]

The fixed effects and patient random effects are similar to Equation (1), and we again set $\gamma = 0$ to account for baseline imbalance. There are four site random effects, with d_h potentially being the most important, as it represents site variation in the longitudinal treatment effect, ie, a site by treatment interaction. It is assumed that

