7. PRIMARY ANALYSES

7.1. *Primary Objective #1: Evaluate the activity of Ibudilast (MN-166: 100 mg/day) versus placebo at 96 weeks as measured by quantitative MRI analysis for whole brain atrophy using brain parenchymal fraction (BPF).*

The first primary objective of the proposed study is to evaluate the activity of Ibudilast (MN-166) versus placebo by assessing the difference in rates of change in brain parenchymal fraction (BPF) between the Ibudilast and placebo treatment groups as measured at baseline, weeks 24, 48, and 96 post randomization. The evaluation of activity is defined as the test of the null hypothesis that the BPF rates of change in the treatment and placebo groups are equal.

The raw data will be summarized graphically, and in the following table:

Table 7.1: Descriptive statistics of BPF over time

Visit	Ibudilast	Placebo
Baseline		
Mean (SD)	x.xx (xx)	x.xx (xx)
Min. – max.	x.xx-x.xx	x.xx-x.xx
missing	xx	xx
Week 24		
Mean (SD)	x.xx (xx)	x.xx (xx)
Min. – max.	x.xx-x.xx	x.xx-x.xx
missing	xx	xx
Week 48		
Mean (SD)	x.xx (xx)	x.xx (xx)
Min. – max.	x.xx-x.xx	x.xx-x.xx
missing	xx	xx
Week 72		
Mean (SD)	x.xx (xx)	x.xx (xx)
Min. – max.	x.xx-x.xx	x.xx-x.xx
missing	xx	xx
Week 96		
Mean (SD)	x.xx (xx)	x.xx (xx)
Min. – max.	x.xx-x.xx	x.xx-x.xx
missing	xx	xx

The null hypothesis can be evaluated based on an assessment of parameter estimates from a linear mixed model (LMM: Laird and Ware, 1982). LMMs are advantageous for longitudinal clinical trials because they can account for dependency due to repeated measures with relatively few parameters, which potentially enhances statistical efficiency. Furthermore, LMMs can accommodate incomplete cases (i.e., missing data), which is expected in this study due to dropout. LMMs are typically estimated using maximum likelihood methods (Verbeke and Molenberghs, 2000) that yield valid inferences with incomplete cases under the widely applicable assumption that the missing data are ignorable (Little and Rubin, 2002).

For this analysis, assuming linear change over time, the LMM can be written in the following manner:

$$Y_{ij} = \alpha + \beta_1 x_{1i} + \beta_2 x_{2i} + \beta_3 t_{ij} x_{3i} + \beta_4 t_{ij} x_{4i} + a_i + b_i + \epsilon_{ij}$$

where:

- Y_{ij} is the BPF value for the j^{th} subject at the j^{th} time point
- α is the common intercept parameter
- t_{ij} denotes time (in weeks)

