- $x_{1i} = 1$ if the subject was thought to be receiving immunomodulation therapy at randomization (IFN/GA), and 0 if the subject was not thought to be receiving immunomodulation therapy
- $x_{2i} = 1$ if the subject was thought to have primary progressive MS at randomization, and 0 if the subject was thought to have secondary progressive MS
- $x_{3i} = 1$ if the subject is in the treatment group
- $x_{4i} = 1$ if the subject is in the placebo group
- a_i and b_i are random effects (random intercepts and slopes)
- ϵ_{ij} is a random error term

After randomization, it is expected that a small number of enrolled subjects may be discovered to fall into a different stratum than that which was thought to be true at the actual time of randomization. For any such subjects, the true strata value discovered post-randomization (not the value thought to be true at the time of randomization) will be used for the models.

Assuming a common intercept constrains the baseline means to be equal, which controls for any initial imbalance that might occur due to empirical randomization (Senn, 2013). We make the typical assumptions:

$$\begin{bmatrix} a_i \\ b_i \end{bmatrix} \sim N(\mathbf{0}, \mathbf{G}), \quad \varepsilon_{ij} \sim N(0, \sigma^2 \mathbf{I}_i), \quad \text{and} \quad \begin{bmatrix} a_i \\ b_i \end{bmatrix} \perp \varepsilon_{ij}$$

In this model, the parameters β_1 and β_2 are included to adjust the model for the two stratification variables (immunomodulation therapy status at randomization & disease status at randomization). The main parameters of interest are β_3 and β_4 , which correspond to the estimated slopes in the treatment and placebo groups, respectively. The desired test of interest can be obtained by testing the null hypothesis of the following contrast:

$$H_0: \theta_1 = \beta_4 - \beta_3 = 0$$

against the alternative

$$H_1: \theta_1 \neq 0.$$

This null hypothesis can be evaluated with the likelihood ratio test, or a Z-test, provided a sufficiently large sample size which is provided in the proposed study. The Z statistic of interest is:

$$Z = \hat{\theta}_1 / SE(\hat{\theta}_1),$$

and leads to the rejection of H_0 when

$$|Z| < Z_{1-\alpha/2}$$

with the latter being the $100(1-\alpha/2)^{\text{th}}$ quartile of the standard normal distribution.

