If we fail to reject H_0 , then we will conclude that there is no significant difference in the change of BPF between the treatment group and the placebo group over 2 years. If H_0 is rejected in favor of the alternative, and θ_1 is greater than zero, then we will conclude that the study provides evidence that the rate of BPF change is slower in the Ibudilast treatment group relative to the placebo group. However, if H_0 is rejected in favor of the alternative, and θ_1 is less than zero, then we will conclude that the study provides evidence that the rate of BPF change is faster in the Ibudilast treatment group relative to the placebo group. It is important to note that failure to reject the null hypothesis does not imply acceptance of the null hypothesis of no difference in slopes over time for the two groups.

The data from the fitted model will be summarized graphically, and in the following table:

Table 7.2: Estimated rate of BPF change by treatment group

Treatment group	Estimated rate of BPF change 90% CI	p-value for difference in rate of change
Ibudilast	xx (xx, xx)	0.xx
Placebo	xx (xx, xx)	

Since the longitudinal measurements will span up to five time points per participant (baseline, 24, 48,

72, and 96 weeks), there is a possibility that the BPF trajectories will not be linear. In order to assess the sensitivity of the results to the assumption of linearity, non-linear trends will be modeled by inserting time as a categorical variable. For this modelling approach, visits that were performed outside of an expected scheduled visit will be categorized into the next expected scheduled visit. We will compare model fit between the non-linear and linear models using the AIC, and will report results from the non-linear model if the AIC suggests that the nonlinear model provides a better fit. In this case, the primary comparison will involve a comparison of the estimated means of the two groups at each time point, and will be displayed in a table similar to the following:

Table 7.3: Model based estimates of BPF over time

Visit	Model Based		p-value for difference
	Ibutilast	Placebo	
Baseline Estimate (SE) 90% CI	xx (xx) (xx, xx)	xx (xx) (xx, xx)	0.xx
Week 24 Estimate (SE) 90% CI	xx (xx) (xx, xx)	xx (xx) (xx, xx)	0.xx
Week 48 Estimate (SE) 90% CI	xx (xx) (xx, xx)	xx (xx) (xx, xx)	0.xx
Week 72 Estimate (SE) 90% CI	xx (xx) (xx, xx)	xx (xx) (xx, xx)	0.xx
Week 96 Estimate (SE) 90% CI	xx (xx) (xx, xx)	xx (xx) (xx, xx)	0.xx

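### If AIC favours categorical time, SAP 7.1 swaps the single primary slope test for a comparison at every visit and gives no rule for success

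*Combined protocol and SAP*

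**What the plan says.** SAP 7.1 starts from one hypothesis: "The evaluation of activity is defined as the test of the null hypothesis that the BPF rates of change" are equal in the two arms. The test is a two-sided slope contrast at 0.10, and the SAP writes out the conclusion for each possible result of that contrast.

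The same section then allows for a non-linear trajectory: "non-linear trends will be modeled by inserting time as a categorical variable". This is introduced as a sensitivity check, but the SAP says it "will report results from the non-linear model if the AIC suggests that the nonlinear model provides a better fit", and that in this case "the primary comparison will involve a comparison of the estimated means of the two groups at each time point". Table 7.3 sets out the result: estimates for each arm and a p-value at Baseline and Weeks 24, 48, 72 and 96.

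On baseline, SAP 7.1 says of the linear model: "Assuming a common intercept constrains the baseline means to be equal". Protocol 12.1.2 states the constraint for the analysis in general: "the baseline group means (intercepts) in the statistical analysis will be constrained to be equal".

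Protocol 12.1.2 handles non-linearity differently. "If polynomials of order greater than one are required", the comparison takes in the extra terms and "an appropriate Wald test will be performed, which is the multiparameter extension" of the Z-test. SAP 7.1 does not carry this over.

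SAP 11.2 (Table 11.1) gives one nominal p-value per look, 0.0104 and 0.0816, and one predictive-power threshold for futility.

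**The concern.** A model fit statistic, computed on the trial's own data, decides which analysis is primary. On one side of the switch there is a single contrast with written conclusions. On the other there are five p-values and no statement of which one, or what combination, decides. Success could be read from any visit, from Week 96, or from a joint test, and the choice would be made with the results in view.

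The gap also reaches the interim look. If AIC switches there, nothing says which visit's p-value is compared with 0.0104 or which contrast drives predictive power.

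Table 7.3 adds a smaller inconsistency. If baseline means are constrained equal, the baseline difference is zero by construction and has no p-value. Either that row is empty or the branch drops the constraint without saying so.

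**Working it through.** **Inputs from the documents.** Two-sided 0.10 (SAP 6 and 7.1); 125 per arm, 1:1 (SAP 1); BPF at 0, 24, 48, 72 and 96 weeks (SAP 2.1, 9.1); final boundary 0.0816 (SAP 11.2).

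**The plan's own figure.** SAP 9.1 gives power close to 80% for a 35% slope difference. Its formula needs the placebo slope, the random-effects covariance and the residual variance. None is printed, so the figure can be neither reproduced nor disputed. The error rates below do not depend on it.

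**How often AIC switches.** Leaving aside the stratification terms, which are the same in both models, the linear model has 3 fixed effects (common intercept, two slopes). Categorical time with a common baseline has 1 + 4 × 2 = 9. AIC prefers it when the likelihood ratio exceeds 2 × (9 − 3) = 12. If the trend is linear, P(χ²₆ > 12) = 0.062.

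**Upper reference.** Four independent post-baseline tests at 0.10 would give 1 − 0.9⁴ = 0.344. The visits are correlated, so the true any-visit figure is lower.

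**Null simulation.** Assumptions: complete data, common baseline, uncorrelated random intercepts and slopes, variances treated as known, 1,000,000 trials per setting. The ratio is the SD of the 96-week slope divided by the residual SD, varied from 0.5 to 10. Intercept SD is 5 times the residual SD in the table; 3 or 10 changes the overall rates by at most 0.001.

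| Ratio | Any visit, linear trend, at 0.10 | Same, at 0.0816 | Any visit when shared curvature forces the switch, at 0.10 |
|---|---|---|---|
| 0.5 | 0.134 | 0.114 | 0.286 |
| 1 | 0.131 | 0.111 | 0.277 |
| 2.5 | 0.125 | 0.104 | 0.240 |
| 5 | 0.115 | 0.095 | 0.195 |
| 10 | 0.108 | 0.088 | 0.154 |

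Other rules, linear trend:
- Joint 4-df test after the switch: 0.126–0.127 at 0.10, 0.106–0.107 at 0.0816. Within switched trials at 0.10 it rejects in about 53%.
- Week 96 after the switch: 0.103 (ratio 0.5) to 0.100 (ratio 10) at 0.10; 0.081–0.084 at 0.0816. Within switched trials at 0.10: 0.14 to 0.10.
- Slope test always kept: 0.100 and 0.081–0.082.

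**Check by hand.** With known variances the slope test is independent of the lack-of-fit statistic, so overall error = 0.938 × 0.10 + 0.062 × (rejection rate within switched trials).
- Joint test: 0.0938 + 0.062 × 0.53 = 0.127.
- Week 96 at ratio 0.5: 0.0938 + 0.062 × 0.14 = 0.1025, against 0.103 simulated.

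The joint test does badly because 3 of the 6 degrees of freedom that AIC examines are the arm-by-visit departures from linearity, and the joint test uses the same 3 plus the slope difference.

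**Check with estimated variances.** Maximum likelihood for all components, 6,000 trials, ratio 0.5, Monte Carlo SE about 0.004: switch 0.065, slope only 0.105, any visit 0.142, joint 0.133, Week 96 0.108.

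**If the branch drops the baseline constraint,** as Table 7.3 suggests: 10 fixed effects, switch when the likelihood ratio exceeds 14, in about 5.1% of trials. Any post-baseline visit then gives 11.0–11.9% with a linear trend and 12–18% under shared curvature; Week 96 gives 10.1–11.2%.

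**Power of Week 96** for a linear effect where the slope test has 80% at 0.10. With constrained baseline: 0.73, 0.75, 0.78, 0.795 and 0.80 across the five ratios. Comparing arm means without the constraint: 0.28–0.77, 0.17–0.72 and 0.12–0.55 for intercept SD 3, 5 and 10.

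**The case against.** The strongest reply is that Week 96 can be inferred. The primary objective is set at 96 weeks, BPF at 48 weeks is ranked tertiary, and no objective uses Week 24 or 72. On that reading overall error is 10.0–10.3% with constrained baseline, so almost nothing is lost. This inference is reasonable, but the branch itself says every time point and gives each a p-value. Protocol 12.1.2 also counts as significant any test that passes the 0.10 level, which does not close off an any-visit reading.

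Second, the SAP's opening text limits interim analyses to the primary endpoint, which Protocol 10.1 defines as a rate of change. That points to the slope for the boundary and futility rule. It does not settle the matter, because SAP 7.1 lets the primary comparison itself change.

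Third, at five scheduled visits a quartic polynomial and categorical time describe the same means, so the protocol's Wald test is close to a joint test for this branch. That is fair, and it means protocol and SAP need reconciling. But the SAP contains no joint test, and one run after an AIC switch does not hold its level when the trend is linear.

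Fourth, the baseline constraint in SAP 7.1 is written for the linear model, and Table 7.3 is only a shell. The general statement in Protocol 12.1.2 still applies, so the conflict stands as a minor point. Without the constraint the any-visit rates are lower than in the table above, but still exceed 10%.

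Last, the variances are assumed, the data complete and the trial exploratory. All true. These points bear on the size of the inflation, not on the missing rule.

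**Conclusion.** The concern holds. SAP 7.1 lets the data replace a fully specified primary test with a set of comparisons that has no decision rule, and this needs no assumed variance to establish. The size does depend on assumptions. With linear change and a constrained baseline, the excess over 10% is at most about 3.5 points (any visit) or 2.7 points (joint test), and close to zero if Week 96 decides. It becomes large, 15–29%, only if both arms share a curved trend and any visit may count; SAP 7.1 itself allows that the trend may curve. The rates at 0.0816 apply that boundary to the final test alone; interim stopping and dropout were not simulated. This should be corrected before unblinding, though it does not undermine the design.

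**What to change.** Keep the linear slope contrast as the sole primary test whatever the AIC, and say that the same contrast is used for the interim boundary and the futility rule. Report the categorical-time model, including Table 7.3, as a sensitivity analysis.

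If a switch is kept, name the Week 96 contrast, with baseline means constrained equal, as the single deciding test; do not use a joint test after an AIC switch. In either case delete the baseline p-value from Table 7.3, and bring the non-linearity paragraphs of Protocol 12.1.2 and SAP 7.1 into line.

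The cost is wording only. The drawback of keeping the slope is that, if trajectories curve, it is only a summary of the arm difference. The drawback of Week 96 is power of 73–80% where the slope test has 80%, provided the baseline constraint is kept.

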7.2.1 Safety

The primary assessment of safety will compare the percentage of subjects in each group with:

- Treatment-emergent adverse events (TEAEs)
- Treatment-emergent serious adverse events (TESAEs)

The main assessment of safety and tolerability will involve a comparison of treatment-related AEs and SAEs across the two treatment groups. First, the percentage of subjects who experience any treatment-related AE in each group will be compared using the following logistic regression model:

$$\text{logit}(Y_i) = \beta_0 + \beta_1 x_{1i} + \beta_2 x_{2i} + \beta_3 x_{3i} + \epsilon_i$$

where

- Y_i represents an indicator of whether or not i^{th} subject had at least one treatment related AE.
- $x_{1i} = 1$ if i^{th} subject was thought to be receiving immunomodulation therapy at randomization (IFN/GA), and 0 if the subject was not thought to be receiving immunomodulation therapy
- $x_{2i} = 1$ if i^{th} subject was thought to have primary progressive MS at randomization, and 0 if the subject was thought to have secondary progressive MS
- $x_{3i} = 1$ if i^{th} subject was randomized to the Ibudilast group, and 0 if the subject was randomized to placebo group
- ϵ_i is random error for the i^{th} subject

To determine if the percentage of subjects having any treatment related AEs differ across treatment group we will test the following hypothesis:

$$H_0: \beta_3 = 0 \text{ vs. } H_A: \beta_3 \neq 0$$

If the null hypothesis is rejected, and $\beta_3 > 0$, we will conclude that Ibudilast was responsible for a significantly greater frequency of treatment-related AEs. Similarly, if $\beta_3 < 0$, we will conclude that Ibudilast was responsible for a significantly lower frequency of treatment-related AEs. In addition to an overall comparison, this hypothesis will be repeated for assessing the percentage of subjects having at least one treatment-related AE within each MedDRA system organ class (SOC). If there are significant differences between groups within any specific SOC, then additional tests will compare differences across groups for specific MedDRA preferred terms in order to further explore the cause of the observed differences.

In addition to the comparison of percentages in the manner described above, the rates of treatment-related AEs in each group will be compared using the following Poisson regression model:

$$\log\left(\frac{Y_i}{T_i}\right) = \beta_0 + \beta_1 x_{1i} + \beta_2 x_{2i} + \beta_3 x_{3i} + \epsilon_i$$

where

- Y_i represents the number of treatment related SAEs experienced by the i^{th} subject.
- T_i represents the number of months between the date of randomization and the date of last follow-up for the i^{th} subject.
- $x_{1i} = 1$ if i^{th} subject was thought to be receiving immunomodulation therapy at randomization (IFN/GA), and 0 if the subject was not thought to be receiving immunomodulation therapy
- $x_{2i} = 1$ if i^{th} subject was thought to have primary progressive MS at randomization, and 0 if the subject was thought to have secondary progressive MS
- $x_{3i} = 1$ if i^{th} subject was randomized to the Ibudilast group, and 0 if the subject was randomized to placebo group
- ϵ_i is random error for the i^{th} subject

To determine if the rate of treatment related SAEs differ across treatment group we will test the following hypothesis:

$$H_0: \beta_3 = 0 \text{ vs. } H_A: \beta_3 \neq 0$$

If the null hypothesis is rejected, the direction of β_3 will indicate the direction of the observed effect. Values of $\beta_3 > 0$ indicate an increased rate of treatment-related AEs associated with the Ibudilast group, while values of $\beta_3 < 0$ indicate a decreased rate of treatment-related AEs associated with the Ibudilast group.

Treatment-related SAEs will be analyzed in the same manner described above. Additional safety analyses will also assess all treatment-emergent AEs, treatment-emergent SAEs, unanticipated SAEs, and treatment-related & unanticipated SAEs in a similar manner.

